- f. Patients may have measurable or non-measurable disease (see [Section 10.1](#)) documented by CT or MRI within 42 days prior to registration. The CT from a combined PET/CT may be used only if it is of diagnostic quality as defined in [Section 10.1a](#). Laboratory parameters are not acceptable as the only evidence of disease. In order to qualify as measurable per [Section 10.1a](#), measurable disease must be outside previous radiation field. All disease must be assessed and documented on the Baseline Tumor Assessment Form (RECIST 1.1).
- g. Patients must have a CT or MRI scan of the brain to evaluate for CNS disease within 42 days prior to registration. Patient must not have symptomatic brain metastases or evidence of leptomeningeal carcinomatosis. Patients with asymptomatic brain metastases are eligible if off of steroids for at least 7 days prior to registration without development of symptoms.

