6.0 STRATIFICATION FACTORS

Patients will be randomized between Arm 1 (afatinib and cetuximab) and Arm 2 (afatinib) using a dynamic balancing algorithm. (24)

Stratification is based on performance status (0-1 vs 2) and EGFR mutation type (exon 19 deletion versus L858R mutation).

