- β Physical exam to include cardiopulmonary examination, examination of abdomen and regional lymph nodes, and assessment of mental and neurological status.
- Ω After off treatment prior to disease progression, scans for disease assessment and physical assessments (with lab tests performed at the discretion of the treating investigator) should take place every 8 weeks until progression.
- % After off treatment following disease progression, physical assessments (with lab tests performed at the discretion of the treating investigator) should take place every 6 months for three years from the time of registration.
- ¥ If institution is participating in repeat biopsy substudy. See [Section 15.5](#) and [15.6](#).
- ◊ Only if patient has brain metastases at baseline.
- § Only if clinically indicated.
- ¶ Diphenhydramine must be given prior to first dose of cetuximab and is recommended prior to subsequent doses (see [Section 7.1](#)).
- ? Vital signs should be checked prior to each cetuximab administration, midway through the infusion, at the completion of the infusion, and one hour post the infusion.
- ã See “Best Practices for SWOG Studies” at the following URL for acceptable time windows for procedures and assessments:
<https://www.swog.org/sites/default/files/docs/2017-10/Best%20Practices%20upddate.pdf>.
- ¿ PET scans are recommended as a complement to other scans (see [Section 10.2d](#)). They are not required.

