10.2 Objective Status at Each Disease Evaluation

Objective Status is to be recorded at each evaluation. All measurable lesions up to a maximum of 2 lesions per organ 5 lesions in total, representative of all involved organs, should be identified as target lesions at baseline. All other lesions (or sites of disease) including any measurable lesions over and above the 5 target lesions should be identified as non-target lesions. Measurements must be provided for target measurable lesions, while presence or absence must be noted for non-target measurable and non-measurable disease.

For studies that use disease progression as an endpoint, whole body scanning at specific intervals is necessary to determine that progression is NOT present outside of the "target" areas. Therefore, in these studies it is not acceptable to image only the "target" areas of the body in follow-up scans. For study-specific imaging requirements, see the Study Calendar in Section 9.0.

- a. **Complete Response (CR):** Complete disappearance of all target and non-target lesions (with the exception of lymph nodes mentioned below). No new lesions. No disease related symptoms. Any lymph nodes (whether target or non-target) must have reduction in short axis to < 1.0 cm. All disease must be assessed using the same technique as baseline.
- b. **Partial Response (PR):** Applies only to patients with at least one measurable lesion. Greater than or equal to 30% decrease under baseline of the sum of appropriate diameters of all target measurable lesions. No unequivocal progression of non-measurable disease. No new lesions. All target measurable lesions must be assessed using the same techniques as baseline.
- c. **Stable:** Does not qualify for CR, PR, Progression or Symptomatic Deterioration. All target measurable lesions must be assessed using the same techniques as baseline.
- d. **Progression:** One or more of the following must occur: 20% increase in the sum of appropriate diameters of target measurable lesions over smallest sum observed (over baseline if no decrease during therapy) using the same techniques as baseline, as well as an absolute increase of at least 0.5 cm. Unequivocal progression of non-measurable disease in the opinion of the treating physician (an explanation must be provided). Appearance of any new lesion/site. Death due to disease without prior documentation of progression and without symptomatic deterioration (see [Section 10.2e](#)).

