10.8 Progression-Free Survival

From date of registration to date of first documentation of progression or symptomatic deterioration (as defined above), or death due to any cause. Patients last known to be alive without report of progression are censored at date of last disease assessment.

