The primary objective for the new design is to compare PFS between the arms at the 1-sided 0.025 level. This analysis would take place when 134 PFS events or 70% of the events among eligible patients have been observed (whichever comes first and will depend on sample size attained). With 134 PFS events, this study has 90% power to detect a hazard ratio of 0.57 (75% improvement). The following table describes the analysis as a function of how many patients are accrued by the time of study closure:

Final Sample Size	# events at analysis	HR with 90% power	improvement in PFS
160	112	0.54	85%
180	126	0.56	78%
200	134	0.57	75%
212	134	0.57	75%

An interim analysis will take place when 64 PFS events have been observed. This analysis will be presented to the SWOG Data and Safety Monitoring Committee at the SWOG Group Meeting closest to this number of events. This analysis will evaluate if there is evidence to recommend early stopping of the study for futility by testing the null hypothesis at the 0.5 level, using a stratified log-rank test. If the p-value is 0.5 or greater, than the recommendation will be that there is insufficient evidence to continue accrual to this study.

Secondary Objectives under the revised design are to compare response rates, OS, time to treatment failure (TTF), time to treatment discontinuation (TTD), and toxicity.

Assuming 212 patients enrolled over 36 months with 14 months of additional follow-up, a one-sided log-rank test with an alpha of 0.025 has 90% power to detect an OS hazard ratio of 0.5, corresponding to a 2-fold increase in median OS, under the exponential distribution. Similarly, if it is assumed that the median TTF is 11 months, and the median TTD is also 11 months, there will be 92% power to detect a 70% increase in medians (hazard ratio of 0.59) for each of these endpoints.

Assuming 85% of patients will have measurable disease, 180 patients will be evaluable for the response comparison between arms. Response rates between the arms will be compared using a chi-squared test of independence at the 1-sided 5% level. With 90 patients per arm, this design has 93% power to detect at least a 22% difference in response rates between the arms and within each arm the rates can be estimated to within 10% with 95% confidence.

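### Baseline brain metastases decide who is scheduled for on-study brain scans but are neither balanced nor adjusted for in the primary PFS comparison, which costs some precision and leaves it open to chance imbalance

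*Combined protocol and SAP*

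**What the plan says.** **Baseline.** Section 5.1g: "Patients must have a CT or MRI scan of the brain to evaluate for CNS disease within 42 days prior to registration". The same criterion admits some patients with brain disease: "Patients with asymptomatic brain metastases are eligible if off of steroids for at least 7 days prior to registration". Status is therefore known for everyone, and both groups can enrol.

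**On study.** Both calendars repeat the brain CT or MRI, on treatment and in follow-up before progression, with the same footnote: "Only if patient has brain metastases at baseline" (9.1 and 9.2). CT of chest and abdomen is scheduled for all.

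**Endpoint.** PFS runs "From date of registration to date of first documentation of progression or symptomatic deterioration (as defined above), or death due to any cause" (10.8). Progression includes "Appearance of any new lesion/site" (10.2d), so a new brain lesion counts.

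**Randomisation.** Allocation is made "using a dynamic balancing algorithm", and "Stratification is based on performance status (0-1 vs 2) and EGFR mutation type (exon 19 deletion versus L858R mutation" (6.0).

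**Analysis.** Section 11.2c compares PFS at the 1-sided 0.025 level and states: "With 134 PFS events, this study has 90% power to detect a hazard ratio of 0.57 (75% improvement". It names a stratified log-rank test for the interim look at 64 events but no test for the final PFS analysis. Section 11.1 names a stratified log-rank test, but for the superseded design. Nothing in Section 11 mentions brain metastases.

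**The concern.** Silent brain progression is looked for on schedule in patients who entered with brain metastases. In the others, the calendar leaves it to be found by symptoms or by unscheduled imaging. The plan's own assessment rules thus tie this baseline factor to the timing of the primary endpoint, in addition to any prognostic effect it has. PFS became the primary endpoint in the revised design, and the two original stratification factors were kept.

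With about 106 patients per arm, an unlisted factor can differ between arms by chance and move the observed hazard ratio. Even with good balance, leaving out a prognostic factor pulls the hazard ratio towards 1 and gives up some of the power that the same events could provide.

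**Working it through.** **1. The plan's own figure.** With 1:1 allocation, Schoenfeld's formula gives events = 4(1.960 + 1.282)² / (ln 0.57)² = 42.03 / 0.316 = 133.0, rounded up to 134. Power at 134 events = Φ(√134/2 × 0.5621 − 1.960) = Φ(1.29) = 0.902. The stated 90% reproduces and does not depend on brain metastases. Freedman's formula would ask for 141 events.

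**2. Assumed inputs.** The documents give no prevalence of brain metastases, no prognostic effect and no CNS share of progressions. Assumed: prevalence p of 20-40% and a PFS hazard ratio for the factor of 1.0-2.0. From the documents: 106 per arm, 134 events, HR 0.57, 36 months of accrual, and control medians of 13.7 and 10.8 months (56% and 44% of patients).

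**3. Chance imbalance.** SD of the difference in proportions = √(2p(1−p)/106); chance of a 10-point gap or more = 2[1 − Φ(0.10/SD)].

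| p | SD | Chance of ≥10 points |
|---|---|---|
| 20% | 5.5 points | 7% |
| 30% | 6.3 points | 11% |
| 40% | 6.7 points | 14% |

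At the smallest sample size in the 11.2c table (160 patients, 80 per arm) and p = 30%, SD = √(0.42/80) = 7.2 points and the chance is about 17%.

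**4. Effect of a 10-point imbalance on the unadjusted HR.** This is approximately (factor HR)^0.10: 1.023 for a factor HR of 1.25, 1.041 for 1.5 and 1.072 for 2.0. A large simulation (35% vs 25%, true HR 1) gave 1.035 and 1.072 for 1.5 and 2.0.

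**5. Power for a true HR of 0.57 at 134 events, simulated.** Model A is a Cox model stratified by performance status and mutation type, without vs with the brain-metastasis covariate (10% PS 2 assumed, 2,500 trials per setting). Model B is a log-rank test, unstratified vs stratified by brain metastases. It adds an assumed 20% CNS share of progressions and a mean 6-month detection delay where no brain scan is scheduled (3,000 trials per setting).

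| Prevalence, factor HR | A: without / with | B: without / with |
|---|---|---|
| no effect (1.0) | 88.0 / 88.0 | – |
| 20%, 1.25 | – | 88.8 / 88.5 |
| 30%, 1.25 | – | 89.0 / 88.9 |
| 30%, 1.5 | 86.2 / 87.0 | 88.5 / 89.0 |
| 20%, 2.0 | – | 87.2 / 89.4 |
| 30%, 2.0 | 85.0 / 88.3 | 84.7 / 87.7 |
| 40%, 2.0 | 84.7 / 88.0 | 85.7 / 88.9 |

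The largest gain is 3.3 points. In A, the mean unadjusted HR is 0.58-0.59 against 0.57 with the covariate. Only the paired differences should be read: even with no factor effect, A gives 88.0%, below the formula's 90.2%.

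**6. Error rates.** Averaged over the nine null settings of model B, 1-sided type I error is 0.025 unstratified and 0.024 stratified (individual settings ran from 0.017 to 0.034). Given a 10-point imbalance (30% prevalence, factor HR 1.5), the unstratified error is 0.009 or 0.042 depending on direction, and power is 0.82 or 0.93. The stratified test holds 0.024-0.025 and 0.88-0.89.

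**7. The imaging schedule alone.** With no prognostic effect, 30% prevalence, a CNS share of 10-30% and a mean detection delay of 3-12 months, the schedule induces a factor HR of only 1.04-1.17. Power without vs with the covariate was 89.7/89.4, 88.7/88.3, 87.9/87.3, 89.9/89.3 and 89.0/89.5, so there is no consistent gain.

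**The case against.** The strongest reply is that nothing here is an error. The footnote is the same in both arms and status is fixed before randomisation, so the factor is balanced in expectation. Overall type I error is near 0.025 and the power figure reproduces. All of this stands.

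Second, the calendar is a weak reason for adjustment. A reader might infer that the imaging rule itself drives the loss, but step 7 shows that it does not. Nearly all the gain comes from an assumed prognostic effect, and that argument applies to any strong prognostic factor. This also stands. What sets this factor apart is that it is recorded for every patient and that the protocol's own assessment schedule depends on it.

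Third, the effect is small. A 10-point imbalance at a factor HR of 2.0 moves 0.57 to 0.57 × 1.072 = 0.61, still well inside the significance boundary of about exp(−1.96 × 2/√134) = 0.71. That is fair for an effect as large as 0.57. It matters more if the observed result falls near the boundary.

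Fourth, the footnote governs scheduled scans only. A reader might infer that other patients never have their brain imaged. The documents do not say so: symptom-driven scans are not forbidden, each cycle's physical examination covers neurological status, and symptomatic deterioration is itself a PFS event.

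Fifth, changing the primary test late has a cost. The appendix title page is marked closed in April 2018, and the afatinib adverse event list is dated June 2020. The documents do not show whether PFS results by arm have been seen, so the condition on timing is essential.

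**Conclusion.** The point holds as a modest improvement. Baseline brain-metastasis status is known for all patients and affects how early silent CNS progression is found, yet it is absent from both randomisation and analysis, and the final PFS test is not named in 11.2c.

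Under the assumed 20-40% prevalence and factor HR of 1.0-2.0, adjustment changes power by about 0 to 4 points (largest simulated gain 3.3), with essentially no loss if the factor has no effect. An imbalance of 10 points or more has a 7-14% chance; a 10-point imbalance would shift the unadjusted HR by about 2-7% for a factor HR of 1.25-2.0. These sizes rest on values that the documents do not give.

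Two stronger readings are not supported. The conditional imaging does not systematically bias the treatment comparison, because the rule is common to both arms. The stated 90% power is not wrong, because it follows from 134 events and HR 0.57.

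**What to change.** Add to 11.2c, before any arm-level PFS results are seen:

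> The final PFS hazard ratio, its confidence interval and the 1-sided 0.025 test will come from a Cox model stratified by performance status and EGFR mutation type, with baseline brain metastases (yes/no) as a covariate. The log-rank test stratified by the two randomisation factors will be reported alongside.

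A covariate is preferable to a third stratification factor: eight strata lost up to about 1 point of power in simulation when the factor was weak. If the sponsor keeps the stratified log-rank test as primary, it should be named with its strata, and the adjusted Cox model should at least supply the pre-specified hazard ratio and confidence interval.

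No new data, scans or patients are needed. The costs are that the hazard ratio becomes conditional on brain-metastasis status, that the final test differs from the interim stratified log-rank test, and that the change must be documented as made before results were seen. Adjustment does not recover CNS progressions missed where no brain scan is scheduled.

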9.2 STUDY CALENDAR – ARM 2: AFATINIB ALONE

REQUIRED STUDIES ^ã	PRE STUDY	Σ																Ω	%		
		Cycle 1				Cycle 2				Cycle 3				Cycle 4							
		W	W	W	W	W	W	W	W	W	W	W	W	W	W	W	W				
PHYSICAL																					
History and Physical Exam ^β	X	X				X				X				X				X			
Weight and Performance Status	X	X	X	X	X	X				X				X				X	X		
Disease Assessment	X									X								X			
Toxicity Notation		X	X	X	X	X				X				X				X	X		
LABORATORY																					
CBC/Differential/Platelets	X	X	X	X	X	X				X				X				X	X		
Serum Sodium and Potassium	X	X	X	X	X	X				X				X				X	X		
Serum Creatinine/ Calculated Creatinine Clearance	X	X	X	X	X	X				X				X				X	X		
Albumin	X	X	X	X	X	X				X				X				X	X		
Total Protein	X	X	X	X	X	X				X				X				X	X		
Serum Bilirubin	X	X	X	X	X	X				X				X				X	X		
Alkaline Phosphatase	X	X	X	X	X	X				X				X				X	X		
AST and ALT	X	X	X	X	X	X				X				X				X	X		
INR ^δ	X	X	X	X	X	X				X				X				X	X		
SPECIMEN SUBMISSION																					
Tissue for banking & correlative studies [£]	X																	X [¥]			
Blood, Buffy coat, & Plasma [£]	X									X								X			

Calendar continues on next page. Click here for [Footnotes](#).

REQUIRED STUDIES ^ã	PRE STUDY	Σ																Ω	%
		Cycle 1				Cycle 2				Cycle 3				Cycle 4				F/U Prior to Prog	F/U After Prog
		W	W	W	W	W	W	W	W	W	W	W	W	W	W	W	W		
X-RAYS AND SCANS																			
PET scan [¿]	X																		
CT of chest and abdomen	X									X								X	
Brain CT or MRI	X								X◊									X◊	
ECHO or MUGA [§]	X																		
ECG [§]	X																		
TREATMENT																			
Afatinib		X	X	X	X	X	X	X	X	X	X	X	X	X	X	X	X		

Footnotes for Calendar 9.2:

- Σ Protocol treatment and physical, laboratory, and scan parameters will continue at the intervals indicated in the Cycle 3 and 4 columns until progression of disease or until patient has met any of the guidelines in [Section 7.6](#).
- £ Required specimen submission for patients. See [Section 15.2-15.4](#) for additional information.
- δ Only if patient is on warfarin.
- β Physical exam to include cardiopulmonary examination, examination of abdomen and regional lymph nodes, and assessment of mental and neurological status.
- Ω After off treatment prior to disease progression, scans for disease assessment and physical assessments (with lab tests performed at the discretion of the treating investigator) should take place every 8 weeks until progression.
- % After off treatment following disease progression, physical assessments (with lab tests performed at the discretion of the treating investigator) should take place every 6 months for three years from the time of registration.
- ¥ If institution is participating in repeat biopsy substudy. See [Section 15.5-15.6](#).
- ◊ Only if patient has brain metastases at baseline.
- § Only if clinically indicated.
- ã See “Best Practices for SWOG Studies” at the following URL for acceptable time windows for procedures and assessments:
<https://www.swog.org/sites/default/files/docs/2017-10/Best%20Practices%20update.pdf>.
- ¿ PET scans are recommended as a complement to other scans (see [Section 10.2d](#)). They are not required.

10.0 CRITERIA FOR EVALUATION AND ENDPOINT ANALYSIS

10.1 Measurability of Lesions

a. **Measurable disease:** Measurable disease is defined differently for lymph nodes compared with other disease and will be addressed in a separate section below.

1. Lesions that can be accurately measured in at least one dimension (longest diameter to be recorded) as ≥ 2.0 cm by chest x-ray, by ≥ 1.0 cm with CT or MRI scans, or ≥ 1.0 cm with calipers by clinical exam. All tumor measurements must be recorded in decimal fractions of centimeters (or millimeters).

The defined measurability of lesions on CT scan is based on the assumption that CT slice thickness is 0.5 cm or less. If CT scans have slice thickness greater than 0.5 cm, the minimum size for a measurable lesion should be twice the slice thickness.

2. A malignant lymph node is to be considered pathologically enlarged and measurable if it measures ≥ 1.5 cm in **SHORT AXIS** (greatest diameter perpendicular to the long axis of the lymph node) when assessed by scan (CT scan slice recommended being no greater than 0.5 cm).

b. **Non-measurable disease:** All other lesions (or sites of disease), including small lesions (longest diameter < 1.0 cm or pathologic lymph nodes with ≥ 1.0 cm to < 1.5 cm short axis), are considered non-measurable disease. Bone lesions, leptomeningeal disease, ascites, pleural/pericardial effusions, lymphangitis cutis/pulmonitis, inflammatory breast disease, and abdominal masses (not followed by CT or MRI), are considered non-measurable as are previously radiated lesions that have not progressed.

c. **Notes on measurability**

1. For CT and MRIs, the same type of scanner should be used and the image acquisition protocol should be followed as closely as possible to prior scans. Body scans should be performed with breath-hold scanning techniques, if possible.
2. PET-CT: At present, the low dose or attenuation correction CT portion of a PET-CT is not always of optimal diagnostic CT quality for use with RECIST measurements. However, if the site can document that the CT performed as part of a PET-CT is of identical diagnostic quality to a diagnostic CT, then the CT portion of the PET-CT can be used for RECIST measurements and can be used interchangeably with conventional CT.
3. Ultrasound: Ultrasound is not useful in assessment of lesion size and should not be used as a method of measurement.
4. Cystic lesions that meet the criteria for radiographically defined simple cysts should not be considered as malignant lesions (neither measurable nor non-measurable) since they are, by definition simple cysts.
5. If a target lesion becomes very small some radiologists indicate that it is too small to measure. If the lesion is actually still present, a default

measurement of 0.5 cm should be applied. If the radiologist believes the lesion has gone, a default measurement of 0.0cm should be recorded.

10.2 Objective Status at Each Disease Evaluation

Objective Status is to be recorded at each evaluation. All measurable lesions up to a maximum of 2 lesions per organ 5 lesions in total, representative of all involved organs, should be identified as target lesions at baseline. All other lesions (or sites of disease) including any measurable lesions over and above the 5 target lesions should be identified as non-target lesions. Measurements must be provided for target measurable lesions, while presence or absence must be noted for non-target measurable and non-measurable disease.

For studies that use disease progression as an endpoint, whole body scanning at specific intervals is necessary to determine that progression is NOT present outside of the "target" areas. Therefore, in these studies it is not acceptable to image only the "target" areas of the body in follow-up scans. For study-specific imaging requirements, see the Study Calendar in Section 9.0.

- a. **Complete Response (CR):** Complete disappearance of all target and non-target lesions (with the exception of lymph nodes mentioned below). No new lesions. No disease related symptoms. Any lymph nodes (whether target or non-target) must have reduction in short axis to < 1.0 cm. All disease must be assessed using the same technique as baseline.
- b. **Partial Response (PR):** Applies only to patients with at least one measurable lesion. Greater than or equal to 30% decrease under baseline of the sum of appropriate diameters of all target measurable lesions. No unequivocal progression of non-measurable disease. No new lesions. All target measurable lesions must be assessed using the same techniques as baseline.
- c. **Stable:** Does not qualify for CR, PR, Progression or Symptomatic Deterioration. All target measurable lesions must be assessed using the same techniques as baseline.
- d. **Progression:** One or more of the following must occur: 20% increase in the sum of appropriate diameters of target measurable lesions over smallest sum observed (over baseline if no decrease during therapy) using the same techniques as baseline, as well as an absolute increase of at least 0.5 cm. Unequivocal progression of non-measurable disease in the opinion of the treating physician (an explanation must be provided). Appearance of any new lesion/site. Death due to disease without prior documentation of progression and without symptomatic deterioration (see [Section 10.2e](#)).

Notes regarding new lesions: FDG-PET imaging can complement regular scans in identifying new lesions according to the following algorithm.

1. Negative FDG-PET at baseline, with a positive FDG-PET at follow-up is a sign of progression based on a new lesion.
2. No FDG-PET at baseline and a positive FDG-PET at follow-up corresponding to a potential new site of disease must have a confirmation by anatomical assessment (e.g. CT, MRI, x-ray) as new site of disease to be considered progressive disease. In such a case, the date of progressive disease will be the date of the initial abnormal FDG-PET.

- e. **Symptomatic deterioration:** Global deterioration of health status requiring discontinuation of treatment without objective evidence of progression. Efforts should be made to obtain objective evidence of progression after discontinuation.
- f. **Assessment inadequate, objective status unknown:** Progression or symptomatic deterioration has not been documented, and one or more target measurable lesions have not been assessed or inconsistent assessment methods were used.
- g. Objective status notes:
 - 1. Non-measurable and non-target measurable disease do not affect Objective Status in determination of CR (must be absent--a patient who otherwise has a CR, but who has non-measurable or non-target measurable disease present or not assessed, will be classified as having a PR). However, non-measurable and non-target lesions are included in determination of progression (if new sites of disease develop or if unequivocal progression occurs in the opinion of the treating physician).
 - 2. An objective status of PR or stable cannot follow one of CR. Stable can follow PR only in the rare case that tumor increases too little to qualify as progression, but enough that a previously documented 30% decrease no longer holds.
 - 3. In cases for which initial flare reaction is possible (hypercalcemia, increased bone pain, erythema of skin lesions), objective status is not progression unless either symptoms persist beyond 4 weeks or there is additional evidence of progression.
 - 4. Lesions that appear to increase in size due to presence of necrotic tissue will not be considered to have progressed.
 - 5. For bone disease documented on bone scan only, increased uptake does not constitute unequivocal progression. However, increase in the soft tissue component of a lesion as measured by CT or MRI would constitute progression.
 - 6. Appearance of new pleural effusions does not constitute unequivocal progression unless cytologically proven of neoplastic origin, since some effusions are a toxicity related to therapy or other medical conditions. Increase in the size of an existing effusion does not constitute unequivocal progression, since the fluid status of the patient could alter the size of the effusion.
 - 7. If CR determination depends on a lesion for which the status is unclear by the required tests, it is recommended the residual lesion be investigated with biopsy or fine needle aspirate.

